Real world applicability of a study is enhanced if exclusion criteria are kept to a minimum. However, clear confounds should be avoided. Miller, et al., found that in young surgical patients, diabetes, cancer, kidney disease, hypertension, and abnormal BMI all significantly increased the chances of wound complications, while COPD, smoking, age, and HIV status did not.⁸² Yang, et al., found that smoking, hypertension, age, diabetes, and obesity did not delay VLU healing, and that males were more likely to have delayed VLU healing.⁸³ In contrast, Lane, et al., found that smoking dramatically reduced pressure injury healing, and McDaniel and Browning found that smoking negatively impacts chronic wound healing by impairing neutrophil function and fibroblast activity; decreasing both white and red blood cell production; increasing carbon monoxide, hydrogen cyanide, and other toxic compounds; causing tissue hypoxia; and causing the release of catecholamines.^{84,85} Smoking cessation programs led to improved wound healing.^{84,85} Parker, et al., found that delayed venous ulcer healing was correlated with living alone, ulcer duration > 24 weeks, and age > 70 years.⁸⁶ A review of studies of venous leg ulcer management demonstrated that 12 weeks were sufficient to determine if a treatment was effective or not.⁸⁷

2. Research Questions/Aim:

This study's primary purpose is to determine if an *improvised dressing*, made from inexpensive materials available for purchase in rural as well as urban settings, is a safe and effective, culturally and medically acceptable choice for managing sickle cell leg ulcers in a tropical climate. Three research questions will be addressed:

(1) Is the *improvised dressing*, consisting of a cut-to-fit new plastic bag sealed at the periwound with zinc oxide paste, safe and effective (see definitions, below) when compared with usual practice (saline-soaked gauze) and when compared with an advanced wound dressing (PMD), on sickle cell leg ulcers (SCLUs) in Jamaica?

(2) Does use of the *improvised dressing*, when compared with usual practice, improve the quality of life of patients (decrease pain, increase ability to engage in desirable activities, decrease wound-related materials costs, decrease time required to perform dressing changes, improve Wound QoL scores, and improve ASCQ-Me pencil-and-paper interview scores) with SCLUs in Jamaica?

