(3) Is the *improvised dressing* culturally acceptable to health care providers, patients, and families for managing SCLUs in Jamaica?

The expected study outcome is improvised dressing superior effectiveness and quality of life, when compared with usual practice, without increased safety and acceptability issues.^{13,59,60,62} The improvised dressing is likely to be the least expensive choice, with the added benefit of being available as first aid treatment throughout Jamaica. The advanced dressing is likely to be more expensive with respect to materials costs, although fewer dressing changes are anticipated and pain medication expenses are likely to be reduced. Based upon the review of the literature, no serious infections or other safety issues are anticipated for any group. However, to ensure that complications are not overlooked, in addition to the onsite researchers' vigilance, weekly wound photos will be assessed for complications (signs of infection, wound deterioration, or clinically relevant maceration) by two off-site blinded wound experts, Drs. [name] and [name].

Definitions:

Sickle cell leg ulcer – a wound in a HbSS or HbS β^0 positive patient, open greater than one month,⁷ below the level of the knee excluding the plantar surface of the foot.

Closed wound -100% epithelialized with no discernible scab or exudate production (paper napkin remains dry when lightly pressed against area, and no recurrence in the subsequent two weeks)

Safe – infection and other complications (healing-impairing maceration, keloid, and contracture rates) not statistically significantly higher than usual practice, with no major adverse events attributable to the method

Effective – ulcer closure rates or ulcer surface area reduction rates not statistically significantly lower than usual practice

Acceptable – average acceptability scores of 4 or higher on a 1-5 scale

3. Methods and Materials

a. Study design

This study will be a targeted-blinded (the off-site wound experts and the local physicians verifying wound closure and/or complications will be blinded to the randomization group), randomized controlled trial with three arms: (1) usual practice (negative control), (2) the improvised dressing, and (3) the advanced dressing (positive control). The expected outcome is improvised and advanced dressing superiority.

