Decrease in SCLU surface area will be used to answer research question 1. Conducting a power analysis for this study is challenging because only one study of SCLUs has demonstrated a statistically significant outcome, and the effect size was obscured by high standard deviations, which is a common problem in studies of wounds.⁸ Improvised plastic dressings similar to the study dressings were used in 49 chronic pressure ulcers in elderly patients, which are often slow to close, if they heal at all.⁶⁰ These two studies demonstrated a significant difference with confidence intervals of 99% with ~25 patients per group. Based upon these sample sizes and the Central Limit Theorem, it is reasonable to set the minimum sample size for this study at 30 patients per group,.^{88,89}

d. Variables

Dependent Variables (measured weekly - tools and permissions in appendices):

- 1. Persistent wound pain (using the Faces Pain Scale Revised (FPS-R))
- 2. Procedural (dressing change) wound pain
- 3. Amount of pain medication taken, including a total number of morphine equivalents plus non-opioid pain medications
- 4. Approximate time spent standing, or sitting with leg dependent without compression (estimated hours per week)
- 5. Patient overall quality of life (assessed with the ASCQ-Me Emotional, Pain, Social Functioning, Stiffness, and Sleep Impact Short Forms)
- 6. Patient wound-specific quality of life (assessed with the Wound QoL tool)
- 7. Materials costs (estimated, using lowest retail costs on Amazon.com for items not on the UWI price sheets)
- 8. Time spent performing dressing changes
- 9. Wound complication rates (e.g., wound infection, healing impairing maceration, wound deterioration)
- 10. Change in wound surface area (measured in cm² electronically using software that automatically corrects for skew, such as HealthEPix or WoundMatrix)⁹⁰

Dependent Variables (measured one time, at graduation from study)

- 11. Wound closure time, in weeks (see definitions; verified two weeks later. Omit patients whose wounds did not fully close they are included in 10., above.)
- 12. Acceptability of dressing choice patient (5 point Likert scale and qualitative free response)
- 13. Acceptability of dressing choice family member (5 point Likert scale and qualitative free response)
- 14. Acceptability of dressing choice UHWI staff (5 point Likert scale and qualitative free response)

Independent Variables (documented at initial study visit):

1. Patient gender

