As a token of appreciation from the research team and an incentive for patients to return for their study clinic visits, each participant will be presented with a 500JM phone card at the end of each of the three 4-week study periods.

All wound management supplies for all three groups will be donated. Shipping and handling fees will be paid by the Principal Investigator with funds from a Wound Healing Foundation grant. Tallies of supplies used at dressing changes will be priced using the cost of medical supplies purchased by the SCU to determine the estimated cost of the treatment supplies for each patient. The PMD rolls will be valued at \$26.99US.⁹⁸

The Principal Investigator will de-identify the data and compile it from the patient Data Collection Tools onto an Excel spreadsheet. This spreadsheet and the de-identified wound photographs will be backed up onto the Principal Investigator's second password protected hard drive via a secure internet connection at least weekly. Two encrypted USB drives containing the data, including wound photographs, will be updated weekly on an alternating schedule and stored in a securely locked file in [name] office in UWI Department of Surgery.

i. Statistical analysis

A consultant, [name], PhD, Senior Biostatistician at The University of Texas Medical Branch in Galveston, will undertake the analysis.

When all of the patients have completed the study, the remainder of the data from the deidentified Data Collection Tools will be transcribed into an Excel spreadsheet by the Principal Investigator. The data will then be evaluated by the biostatistician using the most recent version of SPSS. Groups will be compared with respect to each of the 14 dependent variables, taking into account any confounding from the 11 independent variables. Results will be reported using descriptive statistics (means, modes, medians, frequencies), student's t test, and ANOVA with 95% CIs, using intent-to-treat.¹³ If the improvised dressing does not attain statistical superiority to usual practice, 80% CIs will be calculated with drop-outs removed from the analyses to evaluate noninferiority.^{13, Appendix: From Oczkowski SJW} Complications will be evaluated both individually and collectively by collapsing the pertinent columns.

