Research questions (1) and (2) will be addressed by using analyses of covariance (ANCOVA) to determine if patients in the improvised dressing group (Group 2) had superior results (95% CI's will fall within *f*, the superiority margins) from usual practice (Group 1) or advanced dressings (Group 3), or, if this is not demonstrated, failed to vary significantly (80% CI's will fall within *f*, the inferiority margins) from usual practice (group 1) or advanced dressings (group 3) with respect to each of the dependent variables, controlling for relevant patient characteristics (the independent variables).

Research question (3) will be addressed with descriptive statistics across Likert items regarding endorsement of and concerns with use of the improvised dressing clinically or in future studies. Qualitative comments will be summarized across providers into content themes. Any differences between nurses, patients, family members, and physicians will also be explored and noted.

All health care providers at UHWI participating in the study will be surveyed to explore their concerns as well as their opinions about each dressing choice, using both qualitative open-ended and a quantitative question on a Likert scale. Results will then be shared with the participating clinical staff to provide them with the evidence concerning each of the three dressing protocols.

j. Data handling and record keeping

All study data will be transferred from written documents to the Principal Investigator's password protected electronic devices, de-identified, and then transmitted over secure internet connections to the backup hard drive in the USA. The paper study documentation and the two encrypted USB drives containing the raw data will be stored in a securely locked file in in [name] office in UWI Department of Surgery for a period of at least two years after the study has been published, after which they may be destroyed.

When all of the patients have completed the study, members of the UHWI research team will proofread the Excel spreadsheet with the de-identified data for transcription errors. This data will then be evaluated by the biostatistician using the most recent version of SPSS.

4. Ethical Considerations

This study will be approved by the Ethics Review Committee (ERC) at UWI and the Jamaican Ministry of Health (MOH) prior to its implementation. It will be listed on clinicaltrials.gov prior to the recruitment of the first study patient.

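### 'Effective' can be met on closure or on area, and no primary outcome, question 2 success rule or multiplicity control is stated, so the chance of a false claim of benefit is inflated

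*Combined protocol and SAP*

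**What the plan says.** All references are to the combined protocol and SAP.

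- **Question 1.** Section 2 asks whether the improvised dressing is safe and effective and refers to the definitions that follow. There, 'Effective' means "ulcer closure rates or ulcer surface area reduction rates not statistically significantly lower than usual practice". Section 3c says something narrower: "Decrease in SCLU surface area will be used to answer research question 1".
- **Question 2.** Section 2 asks about quality of life against usual practice. It lists "decrease pain, increase ability to engage in desirable activities, decrease wound-related materials costs, decrease time required to perform dressing changes", followed by better Wound QoL and ASCQ-Me scores. That makes six items joined by 'and'. How many must improve is not stated.
- **Testing.** Section 3i says "Groups will be compared with respect to each of the 14 dependent variables", by "student's t test, and ANOVA with 95% CIs, using intent-to-treat". For questions 1 and 2 it then specifies ANCOVA of Group 2 for superiority over "usual practice (Group 1) or advanced dressings (Group 3"), "with respect to each of the dependent variables, controlling for relevant patient characteristics (the independent variables"). If superiority over usual practice is not reached, "80% CIs will be calculated with drop-outs removed from the analyses to evaluate noninferiority".
- **Question 3.** Section 3i handles acceptability (variables 12 to 14 in section 3d) with descriptive statistics.

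The text labels no outcome as primary, gives no order of testing and no adjustment for multiple tests, and names no analysis time point for the variables that section 3d measures weekly.

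**The concern.** There are two problems.

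First, the rule that decides question 1 differs between sections. Under section 3c, area decides. Under the definition that question 1 itself points to, either outcome is enough. A dressing with significantly less area reduction than usual practice, but without significantly lower closure, would fail under section 3c and pass under the definition.

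Second, nothing separates a confirmatory result from the rest. Each variable is tested at its own unadjusted level, against one comparator or the other, and question 2 has no success rule. The outcome that carries the claim could be chosen once the data are known. At stake is whether a positive report from this trial can be taken at the error rate that a 95% interval suggests.

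**Working it through.** **The plan's own figures.** Section 3f plans about 90 participants and allows for 25% dropout: 90 / (1 − 0.25) = 120, which matches. The 30 per group cannot be re-derived, because no effect size, SD or power is given. With 30 per arm, a two-sided 5% test has 80% power for (1.96 + 0.84) × √(2/30) ≈ 0.72 SD. The plan states no overall type I error, so there is none to reproduce.

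**Inputs**
- Question 2 items: 6, against usual practice only (section 2).
- Dependent variables: 14, of which 3 are acceptability ratings (section 3d). That leaves 14 − 3 = 11.
- Comparators: 2, usual practice and the advanced dressing (section 3i). 11 × 2 = 22 tests.
- Error per test: a 95% interval leaves 2.5% in the direction of benefit. This assumes a superiority margin of zero. Section 3i refers to a margin *f*, but the documents at hand give it no value.
- Correlation between outcomes: not given. A range from 0 to 0.8 is assumed.

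**Chance of at least one false benefit**

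For m independent tests it is 1 − 0.975^m. For m = 6: 1 − 0.975^6 = 0.141. For m = 22: 1 − 0.975^22 = 0.427.

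The 22 tests are not independent, because Group 2 enters all of them. Simulation (200,000 runs, three equal arms, no true differences, equal correlation between outcomes) gives:

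| Correlation between outcomes | 6 tests, Group 2 v Group 1 | 22 tests, shared Group 2 |
|---|---|---|
| 0 | 14% | 40% |
| 0.5 | 10% | 25% |
| 0.8 | 7% | 15% |

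A single test carries 2.5%.

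**Question 1 under the definition of 'Effective'**

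This rule is passed by the absence of a significant deficit, so the relevant error is passing a dressing that is truly worse. Assume a true deficit of 0.5 SD on each outcome, 30 per arm, and a two-sample t test at two-sided 5%.

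- Noncentrality: 0.5 × √(30/2) = 1.94. Critical value on 58 degrees of freedom: 2.00.
- Chance of being significantly lower: 0.478.
- One outcome passes: 1 − 0.478 = 0.522, about 52%.
- At least one of two independent outcomes passes: 1 − 0.478² = 0.772, about 77%.

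A normal approximation gives 51% and 76%. With the two outcomes correlated at 0.5 or 0.8, 40,000 simulated trials give about 69% and 63%. Closure is a yes/no outcome, so putting it on an SD scale is only an illustration.

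**The case against.** The strongest reply is that the plan is narrower than a literal reading of section 3i. Four parts of it stand.

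- **Any one of six.** A reader might infer that question 2 succeeds if any single item improves. The list is joined by 'and', and no such rule is written. If all six had to improve, the error would not be inflated at all. What can be said is that the rule is missing, and that section 3i tests each variable separately.
- **28 tests.** Fourteen variables times two comparators follows section 3i word for word. But the acceptability ratings belong to question 3, which is descriptive, so 22 is the fairer count.
- **Free choice of comparator.** Question 2 and the definition of 'Effective' both name usual practice only. Question 1 asks about usual practice and the advanced dressing. Only the 'or' in section 3i leaves the choice open.
- **Error of 5% per test.** That counts false differences in either direction. It gives 26% for six independent tests (1 − 0.95^6) and 76% for 28 (1 − 0.95^28), but those are not rates of false benefit. A non-zero superiority margin would lower the rate further.

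It can also be said that section 3c settles question 1 by naming area. It does not, because question 1 sends the reader to the definitions, where closure is an alternative.

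**Conclusion.** The point holds as a conflict between sections and a missing error-control rule. As written, a dressing significantly worse on area can be called effective. The chance of at least one false benefit is about 7% to 14% for the six question 2 items if any one of them may carry the claim, and about 15% to 40% over 22 tests, against 2.5% for a single test. These figures assume a zero superiority margin, no true differences, and correlations between 0 and 0.8.

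A reader might go further and conclude that a false claim of benefit is likely. The documents do not support that. Counting false benefits only, the figure passes one half only for 28 fully independent tests (1 − 0.975^28 = 51%), and the tests share Group 2. 'Inflated' is the right word.

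Some features could push the true figure up and are not in the calculation: several measures per question 2 item, weekly repeats without a named time point, and the fallback to 80% intervals, which leaves 10% on each side.

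**What to change.** 1. **Question 1.** Reconcile the definition of 'Effective' with section 3c by naming one confirmatory test: change in ulcer area from baseline to week 12, Group 2 against Group 1, by ANCOVA in the intent-to-treat set. Section 3h ends data collection once an ulcer has been closed for two weeks, so state that area counts as zero for ulcers verified as closed before week 12. Remove the closure alternative from the definition and report closure as key secondary. Removing it is not enough alone: an area result that is merely not significantly lower would still pass about 52% of the time in the example above. The named test should therefore decide the question.
2. **Question 2.** Name one measure and one time point for each of the six items. This is needed because pain spans variables 1 to 3 in section 3d, ASCQ-Me comprises five short forms, and no variable plainly measures desirable activities. Test Group 2 against Group 1 only, with Holm's procedure across the six: the smallest p value against 0.05/6 = 0.0083, the next against 0.05/5 = 0.01, and so on up to 0.05.
3. **Everything else.** Report the remaining variables and all Group 3 comparisons as estimates with 95% intervals, without significance claims.

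The cost is a wording change, with no new patients or measurements. The question 1 test keeps its full 5% level. The downside is that some question 2 outcomes will need a smaller p value to be claimed.

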- Based upon previous studies and the Central Limit Theorem, an estimated 90 participants (~30 per group) may be required for the differences between groups to reach statistical significance.^{12,23,88,89,96} Up to 120 patients will be recruited to allow for a 25% dropout rate. Based upon the literature review, pain, costs, wound size, and quality of life are expected to be significantly improved using the improvised dressings. However, because SCLUs are, historically, very slow to heal and often enlarge, complete wound closure is not an expected outcome for all patients.

g. Procedures for recruitment and consent

The study will be advertised using free community information channels such as church bulletins and radio outlets. Social media sites such as the CAIHR Facebook page will also be employed. Qualifying patients in the SCU database from up to two years prior to the study initiation will be called by the UHWI surgical team, alerting them to the dates for registering to participate. Flyers will be posted at the SCU in advance. Consent will be obtained by a member of the research team while the potential participant is waiting to be seen for wound care.

h. Data collection

The site for this study is the surgical clinic dressing area at the University Hospital of the West Indies (UHWI), Mona, Jamaica. The adjacent Sickle Cell Unit (SCU) will refer any SCLU patients to UHWI during the study period. UHWI is consistently well staffed with competent Jamaican health professionals. The UHWI surgical team will lead the study. Relatively few Jamaicans live or work in air-conditioned environments, ^[data in appendices] allowing the results from this out-patient population to translate to less developed tropical countries.

To ensure consistency, members of the research team will practice until they can demonstrate competency with all three dressing change procedures and with explaining the study forms prior to study patient recruitment.

Enrollment in the study will begin within two weeks of the day the Principal Investigator arrives at the Mona campus and will close 60 days later, or when a maximum of 120 patients have enrolled. All sickle cell positive patients presenting to UHWI with lower leg ulcers during the enrollment period will be screened for eligibility to enter the study. Each patient's data will be recorded for a total of 12 weeks, or until their SCLU has been closed for 2 weeks, whichever comes first.

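### Weekly outcomes are assigned t tests, ANOVA and ANCOVA with no stated way to use the repeated measurements or keep dropouts in the intent-to-treat analysis; a baseline-adjusted mixed model would do most of this cheaply

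*Combined protocol and SAP*

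**What the plan says.** Section 3d splits the 14 outcomes under two headings. Items 1 to 10 fall under "Dependent Variables (measured weekly - tools and permissions in appendices" and items 11 to 14 (closure time and three acceptability ratings) under "Dependent Variables (measured one time, at graduation from study". Section 3c links the first research question to ulcer area: "Decrease in SCLU surface area will be used to answer research question 1". It names no visit for that comparison.

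On follow-up, section 3h says each patient's "data will be recorded for a total of 12 weeks, or until their SCLU has been closed for 2 weeks", whichever is sooner. The same section withdraws patients who, on evaluation of a possible complication, have not improved on prescribed treatment. Anyone who leaves the assigned group receives usual treatment for the rest of the 12 weeks; whether measurement continues is not stated.

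On numbers, section 3f says: "Up to 120 patients will be recruited to allow for a 25% dropout rate". Section 5 accepts that dropout may be substantial.

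On analysis, section 3i lists descriptive statistics, then "student's t test, and ANOVA with 95% CIs, using intent-to-treat". It adds: "Research questions (1) and (2) will be addressed by using analyses of covariance (ANCOVA"), adjusting for the baseline variables. Dropouts are expressly removed only in the fallback non-inferiority analysis. Sections 3a to 3i contain no repeated-measures model, summary statistic, imputation or other missing-data rule.

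**The concern.** A t test, ANOVA or ordinary ANCOVA takes one outcome value per patient. With up to twelve values per patient, the plan must say which one is used or how they are combined, and it does not. The most direct reading in practice is the week-12 value. A patient without that value then drops out of the analysis unless some method keeps them in, and none is given. The intent-to-treat label would then cover a completers' comparison.

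This matters because leaving is unlikely to be unrelated to healing:

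- Patients who fail to improve can be withdrawn (section 3h), and discouraged patients may leave (section 5).
- Patients know their dressing (section 5), and usual practice is expected to be more painful and slower to apply (section 4). Unequal dropout by arm is therefore plausible.
- Patients whose ulcers close leave two weeks later, so their later values are also absent.

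A week-12 comparison can thus lose both the worst and the best courses. If failing patients leave mainly from usual practice, a real benefit of the improvised dressing shrinks; if mainly from the improvised arm, a benefit can appear where there is none. The contrast in section 3a between an intent-to-treat superiority analysis and a per-protocol non-inferiority analysis would also largely collapse.

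**Working it through.** **1. The plan's own figure.** 90 / (1 − 0.25) = 120, or 40 per arm falling to 30. This reproduces exactly. The 30 per group cannot be derived, because no effect size, SD or power is stated. For reference, with two-sided alpha 0.05 and 80% power, the detectable difference is (1.960 + 0.842) × √(2/30) = 0.72 residual SD.

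**2. Information in one visit.** Assume equal correlation ρ among baseline and the 12 weekly values, with unit variance. The residual variance after baseline adjustment is 1 − ρ² for the last value and (1 + 11ρ)/12 − ρ² for the 12-week mean.

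| ρ (assumed) | Last value | 12-week mean | Mean ÷ last |
|---|---|---|---|
| 0.5 | 0.750 | 0.292 | 0.39 |
| 0.7 | 0.510 | 0.235 | 0.46 |
| 0.8 | 0.360 | 0.177 | 0.49 |
| 0.9 | 0.190 | 0.098 | 0.52 |

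Using one visit leaves 11 of 12 readings (92%) unused but loses 48% to 61% of the information. The two measures also estimate different things: the effect at week 12, and the average effect over the period.

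**3. Precision at week 12 with random dropout.** Take 40 per arm, 25% dropout spread evenly, and compare a mixed model on all available data with ANCOVA on 30 completers per arm. Under equal correlation (0.5 to 0.9) and autoregressive correlation (0.90 to 0.98), the variance falls by 5.9% to 12.6%. Effective n rises from 30 to between 31.9 and 34.3 per arm. The detectable difference becomes 2.802 × √(2/31.9) = 0.70 to 2.802 × √(2/34.3) = 0.68 SD.

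A separate simulation of log area used a random-slope SD of 0.05 per week, residual SD 0.2, an effect of −0.45 at week 12, 22% to 27% dropout and 800 trials. Power was 76% for completers and 85% for the mixed model. That implies a variance reduction of about 1 − [(1.960 + 0.706)/(1.960 + 1.036)]² = 21%. Starting from the same 76%, a 6% to 13% reduction would give about 79% to 82%.

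**4. Bias when dropout is related to outcome.** In the log-area simulation with no true effect, enlarging ulcers dropped out more in one arm, depending on recorded values. The completers' mean was −0.133 (e^−0.133 = 0.875, so about 12% smaller area), with 13.1% rejections. The mixed model gave 0.000 and 4.1%.

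A second simulation used 40 per arm, 1,500 runs, random-intercept SD 0.8, slope SD 0.05 per week and residual SD 0.35. The week-12 SD is √(0.64 + 0.36 + 0.1225) = 1.06. The true difference was −0.50.

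| Dropout (usual practice / improvised) | Completers | Mixed model |
|---|---|---|
| Random, 25% / 25% | −0.502 | −0.501 |
| Follows recorded worsening, 25% / 25% | −0.489 | −0.496 |
| Follows recorded worsening, 35% / 15% | −0.384 | −0.503 |
| Follows unrecorded worsening, 35% / 15% | −0.372 | −0.467 |
| Same, stronger dependence | −0.333 | −0.441 |

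The completers' bias is about 0.12 in the third row and 0.13 to 0.17 in the last two. The mixed model's is nil in the third row and 0.03 to 0.06 in the last two. With equal dropout in both arms, completers show almost no bias: the problem needs dropout that is both outcome-related and unequal. Both simulations gave the mixed model the true covariance, which flatters it. Neither modelled early exit after closure.

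**The case against.** The strongest reply is that the plan is incomplete on this point rather than wrong. Four inferences that a reader might draw go further than the documents allow.

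- **That the plan prescribes a single-value analysis.** It does not. ANCOVA on a 12-week mean, slope or area under the curve would fit section 3i and use every visit.
- **That the analysis cannot be intent-to-treat.** It could be, with multiple imputation or with measurement continued after a patient leaves the assigned dressing. Removing dropouts only for non-inferiority suggests that they are meant to stay in for superiority. What is missing is a method that keeps them.
- **That inflating 90 to 120 proves a completers' analysis.** Trials analysed with mixed models inflate in the same way.
- **That most of the information is discarded.** That is true of the count of readings if one visit is used. In information terms the loss is about half, and it depends on an unstated correlation.

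It is also fair that the simulated figures rest on assumed variances and dropout patterns, and that a stated summary measure with imputation would be an acceptable alternative. The appendices cited in the plan were not available for this review, but the pointers in sections 3a and 3i on analysis concern non-inferiority.

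What stands is that the text gives neither a visit, nor a summary, nor a method for dropouts, in a trial whose own rules make missing values depend on outcome.

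**Conclusion.** The point holds as a low-cost improvement. For ten of 14 outcomes, including the area outcome that carries research question 1, the named tests have no stated link to the weekly series and no means of honouring the intent-to-treat label. If they are run on available week-12 values, about 30 of 120 patients would be left out at the planned dropout rate.

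Bias is the stronger argument. Under unequal dropout that follows recorded outcomes, it was about 0.12 to 0.13 units for completers and absent for the mixed model. The precision gain is modest: 6% to 13% of variance in most settings tried, and about 21% with marked patient-specific slopes and the covariance taken as known.

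A reader might infer that a mixed model settles the matter. It does not. It is valid only if dropout is explained by recorded data, and a bias of 0.03 to 0.06 remained when it was not. If data stop at withdrawal, it estimates the effect as though patients had stayed on their dressing. It does nothing for the four once-only outcomes, including closure time, from which section 3d omits unclosed wounds. Left uncoded, early-closed wounds would be treated as missing and extrapolated, although their area at exit is known.

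**What to change.** Amend section 3i as follows.

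1. For each continuous weekly outcome (items 1 to 8 and 10), make the main analysis a linear mixed model in all randomised patients (SPSS MIXED), with group, week, group by week and the baseline value. Use a parsimonious covariance, such as random intercept and slope. An unstructured matrix over 12 weeks has 12 × 13 / 2 = 78 parameters, too many for 90 to 120 patients with dropout.
2. Name the week-12 contrast of group 2 against group 1 as the result. If a summary measure is preferred, state and justify it, with its missing-data method.
3. Enter verified closed wounds as area zero through week 12, unless a recurrence has been recorded. Analyse area on a pre-named scale that allows zero, for example as a proportion of initial area; the log does not.
4. Analyse complications (item 9) with a binary or event model.
5. State whether outcomes are measured after a patient leaves the assigned dressing, and use any such measurements.
6. Add a sensitivity analysis that assumes no improvement, or a range of delta shifts, for dropouts.
7. Keep t tests and ANOVA as descriptive support.

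The cost is revised wording and slightly more analysis work, with no new data and no change to the 90 or 120. The price is reliance on a missing-at-random assumption, which item 6 probes.
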